decreased DA caused by decreased prefrontal-striatal glutamatergic neurotransmission [44, 85, 86, 92]. Nonparametric Spearman correlation analysis showed that the pretreatment gating effect by the dorsal striatum on the connection from IFC to PPC was inversely related to the Treatment Effectiveness score (TES), a measure of relative abstinence from cocaine use, after 8 weeks of treatment with OA enhancing medications ( $r = -0.69$ ,  $p=0.12$ , see figure in this section). These preliminary findings are consistent with the theory that OA enhancement may be a useful target for pharmacotherapy of cocaine dependence in COs who have pretreatment hypodopaminergic state [81, 88, 89]. A recent study by Martinez et al. [87] showed that low pretreatment striatal OA transmission in COs was associated with treatment failure from behavioral therapy alone (without any pharmacological treatment). One may speculate that COs with low pretreatment OA in that study would benefit from the addition of OA enhancing medication [44]. The results of [87] and our preliminary findings are consistent with the theory that preexisting differences between COs in OA circuits may be a mechanism underlying variability in responsiveness to different treatments [44]. *This pilot study supports our expertise in the use of snDCM and Hypotheses 1 and 2.*

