Urn randomization [153], a form of stratified randomization, will help ensure comparability of treatment groups on baseline severity and duration of cocaine abuse. Pretreatment task behavioral performance or demographic variables on which group differences are detected, and which are correlated with outcomes, meet the definition of confounders [192, 193]. In such cases, analyses will evaluate the robustness of findings after statistically controlling for the confounder. If conclusions remain unchanged after covarying for the confounder, the more parsimonious model will be reported along with a statement indicating its robustness to covariation for potential confounding. If inclusion of the covariate alters the conclusions of the analysis, both models will be reported. Treatment success is a function of two elements: (a) retention and (b) demonstrating cocaine-free status using the SRPHK1 criteria (see section C.3.4). The Treatment Effectiveness Score (TES) provides a metric for this composite outcome [194]. TES is the sum of all cocaine-negative tests (according to SRPHK1 rules). Higher TES indicates that participants both continue to participate in the study and are negative for cocaine. For each group, BMA (section C.4.19.4) is conducted across all OCMs in the model space. Group difference in the gating effect by the dorsal striatum is assessed using Bayesian confidence probability [195]. In addition, BMA is conducted across all OCMs in the model space for each subject in the medication group and in the placebo group. Evaluation of differential treatment response, measured by the TES, as a function of the averaged (across the OCM model space) gating effect, will use Poisson regression. Violations of assumptions of dispersion will result in the use of more appropriate approaches such as zero-inflated Poisson, negative binomial, or zero-inflated negative binomial models. Regression of treatment, averaged gating, and their interaction will permit evaluation of differential treatment response as function of gating. The critical element in doing so is the evaluation of the interaction term. Given that the current study is powered to detect group differences, it is likely underpowered to detect an interaction. Brookes, et al. [196] demonstrate that for studies with 80% power to detect a between-groups effect, power to detect an interaction effect of the same magnitude as the main effect is approximately 29%. One solution is to adopt a Bayesian subgroup analysis approach [197-201]. This approach utilizes the posterior distribution of the interaction parameter to estimate the

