
probability that it exceeds some number (e.g., for Poisson regression a Risk Ratio of 1.0). Specification of vague neutral priors will reflect uncertainty regarding parameter values, utilizing prior distributions for the lower order effects that are neutral and diffuse with specification  $-N(0, 1 \times 10^{-6})$  on the log scale (i.e., centered at the null hypothesis with a 95% Credible Interval of  $\pm 1960$ ) for all coefficients, and  $-U(0, 100)$  for any required dispersion terms. Examination of the interaction of treatment and the subgroup index forms the crux of the evaluation of the subgroup effect. For evaluating the interaction representing the differential subgroup effect, analysis will be conducted in two ways: (a) utilizing diffuse, indifferent priors  $(-N(0, 1 \times 10^{-6})$  on the log scale for the interaction coefficients, and (b) using informative skeptical priors for the coefficients will evaluate sensitivity of statistical conclusions to specification of priors. Informative, skeptical priors will be derived via the method first proposed by Dixon and Simon [200]. Evaluation of resulting posterior distributions will permit conclusions regarding the probability that subgroup/interaction effects of varying magnitudes obtain. Examples of this use of the posterior distribution may be found in Green et al. [197]. Bayesian modeling will use SAS v9.2 (Proc Genmod and Proc Monte-Carlo Markov chain [MCMC]), and in WinBugs 1.4.3 (<http://www.mrc-bsu.cam.ac.uk/bugs>). Convergence of Bayesian analyses on the posterior distributions via MCMC will be assessed via graphical (Trace Plot, Autocorrelation Plot) and quantitative (Geweke Diagnostics, Gelman-Rubin Diagnostics, and Heidelberger-Welsh Diagnostics) evidence. Evaluation of posterior distributions will permit statements regarding the probability that effects of varying magnitudes exist, given the data.

While the use of urn randomization [153] will likely result in comparable groups, substantial heterogeneity may still exist within conditions on baseline variables such as severity, duration of use, and impulsivity. We propose subgroup analyses following the procedures described above. This will determine the degree to which baseline variables moderate the interaction of treatment and snOCM.

Specific Aim 3: To conduct an snOCM of impulsivity to test Hypotheses 1 and 2 (above).

The statistical analysis is essentially the same as in Specific Aims 1 and 2.

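### Differential response to medication is judged only on a ratio scale, so if low-gating patients do worse on placebo, an equal gain in negative tests tends to look like a low-gating advantage

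*Protocol*

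**What the plan says.** Protocol C.4.20 (Specific Aim 2) defines the outcome as a count: "TES is the sum of all cocaine-negative tests (according to SRPHK1 rules". Differential response in TES is examined "as a function of the averaged (across the OCM model space) gating effect, will use Poisson regression", and if the dispersion assumption fails the alternatives are "zero-inflated Poisson, negative binomial, or zero-inflated negative binomial models". The model contains treatment, gating and their product: "Regression of treatment, averaged gating, and their interaction will permit evaluation of differential treatment response as function of gating". Of the product the section says: "The critical element in doing so is the evaluation of the interaction term".

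The Bayesian version puts the priors for the coefficients on the log scale. It summarises the interaction by its posterior probability relative to a reference value, for which the example is "for Poisson regression a Risk Ratio of 1.0". The link function is not named, but this wording implies a log link. The SAP's data analysis plan repeats the same text, and Specific Aim 3 adopts essentially the same analysis.

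Neither document asks for expected TES by arm across gating or for a contrast in negative tests. Neither explains why the ratio scale should define differential response.

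On the background, C.4.20 ties the gating effect to low dopamine. C.2.4, like A.5, cites a study in which "low pretreatment striatal OA transmission in COs was associated with treatment failure from behavioral therapy alone" (OA and COs are scanning errors for DA, dopamine, and CDs, cocaine-dependent subjects). Under C.3.3 weekly cognitive behavioural therapy is the platform for the trial, so placebo patients receive behavioural therapy without active drug.

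**The concern.** With a log link, no interaction means that the drug multiplies expected TES by the same factor at every level of gating. That differs from adding the same number of negative tests at every level, unless expected placebo TES does not vary with gating.

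If low gating marks low dopamine, and low dopamine goes with failure on behavioural therapy alone, placebo TES should be lower at low gating. The same absolute gain is then a larger multiple for low-gating patients, and the product term moves in the hypothesised direction although nobody gains more tests than anyone else.

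The stated purpose is a biomarker that predicts response to dopamine medication. A marker that only separates good from poor prognosis could look, on the ratio scale alone, like one that identifies who gains more from the drug.

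**Working it through.** **The plan's own figure.** C.4.20 gives about 29% power for an interaction as large as a main effect that has 80% power. The interaction contrast has twice the standard error, so power = Φ((1.960 + 0.842)/2 − 1.960) = Φ(−0.559) = 28.8%. This reproduces. It concerns precision and does not bear on the choice of scale.

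**Inputs from the documents.** 24 analysable subjects per group (C.4.1); 12 weeks × 3 visits = 36 scheduled tests (C.3.3); outcome and model as in C.4.20.

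**Inputs not in the documents.** Mean placebo TES by gating level, the drug's effect and the dispersion are all assumptions, varied below.

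**Arithmetic.** Let m_L and m_H be mean placebo TES at low and high gating, and let the drug add *a* tests for everyone. The ratio of drug ratios, low over high gating, is

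R = (1 + a/m_L) / (1 + a/m_H).

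For a > 0, R exceeds 1 exactly when m_L < m_H.

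| Placebo low / high | Gain low / high | Drug ratios low / high | R |
|---|---|---|---|
| 10 / 14 | 3 / 3 | 1.300 / 1.214 | 1.07 |
| 8 / 16 | 6 / 6 | 1.750 / 1.375 | 1.27 |
| 6 / 18 | 9 / 9 | 2.500 / 1.500 | 1.67 |
| 12 / 12 | 6 / 6 | 1.500 / 1.500 | 1.00 |
| 16 / 8 | 6 / 6 | 1.375 / 1.750 | 0.79 |
| 8 / 16 | 6 / 8 | 1.750 / 1.500 | 1.17 |

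In the last row high-gating patients gain more tests, yet the ratio scale still favours low gating.

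**How often this would show at 24 per arm.** One simulation took a placebo mean of 12, rising by 4 per SD of gating (8 and 16 at ±1 SD), and 6 extra tests for all on drug. The posterior probability of an interaction favouring low gating was approximated from the likelihood with flat priors:

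| Counts | Scale | Median probability | Trials above 0.95 |
|---|---|---|---|
| Pure Poisson | Ratio | 0.91 | 40% |
| Pure Poisson | Difference | 0.50 | 4.7% |
| Strongly overdispersed, scaled SE | Ratio | 0.69 | 10.8% |
| Strongly overdispersed, scaled SE | Difference | 0.50 | 3.1% |

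With placebo TES flat in gating, the ratio-scale median returned to about 0.50, with about 5% of trials above 0.95. With the gradient reversed and 6 extra tests, the median fell to 0.08 (Poisson) and 0.28 (overdispersed).

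A second simulation varied the placebo pairs from 8/16 to 4/16 and the gain from 4 to 8 tests, with gamma-Poisson dispersion 0.3 and a scaled Poisson fit. About 5-25% of trials passed a one-sided 0.975 criterion, against about 3% when placebo TES was flat. The upper end is approximate and comes from the steepest assumed gradients.

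These counts were deliberately not truncated at 36. Truncation raises the range to 7-35%, but it trims drug-arm counts most at high gating. With 8/16 and a gain of 8, the gains actually realised become 7.7 and 6.3. Benefit is then no longer equal, so those figures do not describe the equal-gain case.

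**The case against.** The strongest reply is that the plan's pilot points to a pattern in which scale hardly matters. In C.2.4, six patients on dopamine-enhancing drugs showed an inverse relation between gating and TES (r = −0.69, p = 0.12). If TES falls with gating on drug and rises with gating on placebo, low gating is favoured on both scales. Under equal gains, TES on drug instead rises with gating (14 against 22 for the 8/16 pair with +6), and a look at the medication arm would usually show this. In the simulated equal-gain scenarios, the medication-arm correlation had the hypothesised negative sign in only 0-7% of trials. C.4.21 bases the Aim 2 power on just such a correlation, and the planned regression yields the medication-arm slope.

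This stands in part. A reader might infer that the planned analysis cannot distinguish a prognostic marker from a predictive one. The documents do not support that, because the fitted model contains the needed information. However, C.4.20 does not make the medication-arm slope a condition for any claim, and a pilot of six patients on three different drugs does not settle the pattern.

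Three further objections hold. The placebo gradient is indirect: it comes from a cited study of striatal dopamine, linked to gating by treating gating as a dopamine indicator, and no TES by gating level is given. The plan sets no posterior threshold, and its sceptical prior would shrink the interaction, although shrinkage does not change the scale. Finally, a ratio-scale interaction is a legitimate estimand for a count.

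**Conclusion.** The point holds as a conditional one. The plan evaluates differential response on the ratio scale only. If placebo TES is lower at low gating, equal absolute benefit shifts the interaction towards the hypothesised direction. Under the assumed TES levels and overdispersed counts at 24 per arm, about 5-25% of trials would pass an illustrative one-sided 0.975 criterion, against 2.5% nominal. The size depends on the assumed placebo gradient, gain and dispersion. With a flat gradient the effect is nil, and with a reversed gradient it changes sign.

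Two stronger readings are tempting. One is that the trial would wrongly declare gating a predictive biomarker. The figures do not show this: about 75-95% of equal-gain trials would not pass even the illustrative criterion, and the plan has no pass mark. The other is that the ratio interaction is the wrong analysis. It is not; what is missing is the absolute contrast beside it.

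**What to change.** Keep the planned model and both sets of priors. From the same posterior draws, also report:

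- expected TES by arm across gating;
- the medication-minus-placebo difference in expected TES at the 25th and 75th percentiles of gating;
- the difference between those two differences, with a 95% interval and its posterior probability.

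State in the SAP that gating will be described without qualification as predicting greater benefit from medication only when the ratio and absolute contrasts point the same way. Otherwise the interaction is reported as scale-dependent. The same wording should cover Specific Aim 3.

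The cost is a little post-processing, a paragraph of SAP text and a somewhat more cautious conclusion. No new data are needed.

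A hard rule that both contrasts must pass a threshold is not proposed. In simulation it cut claims under equal gains to 2-5%. Where benefit truly differed, it cost little under a pilot-type pattern (claims fell from 80% to 76%) but more when TES on drug was flat in gating (57% to 38%). That is a trade-off for the sponsor in an analysis the plan already calls underpowered, and it would need a threshold that the plan does not have.

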#### 1.b Sources of Materials

Urine, blood, and breath samples will be collected from all recruited subjects. We will also collect demographic information as well as other information needed for screenings, e.g., family history information, and drug use information, from all recruited subjects. In addition, MRI data will be collected from all recruited subjects. All data collected from the subjects will remain confidential. Data recorded by paper will be kept in a locked cabinet in the Principal Investigator's laboratory. Electronic data will be stored in computer, COs or hard disks with password protection. Only the Principal Investigator and trained research assistants will have access.

#### 1.c. Potential Risks

**Phlebotomy:** There is the potential risk of bruising at the site of the blood draw for the HIV test and for the blood chemistries and complete blood count.

**Contraindication to MRI scanner:** Individuals who have pacemakers, metal or electromechanical implants or metallic foreign bodies can be injured if they undergo an MRI scan.

**Claustrophobia:** Some individuals become anxious due to claustrophobia during MRI scans.

**Privacy of individuals:** There is potential risk to privacy of individuals.

**Pregnant women:** There is unknown risk of MRI in pregnancy.

### **2 Adequacy of Protection Against Risks**

#### 2.a Recruitment and Informed Consent

Participants for the Ongoing Clinical Trial (R01 DA030787; [name], EJj will be self-referred in response to various study advertisements. Individuals who call for information will be given a brief description of the study. Those interested will then be asked to answer questions about their current substance use. A trained research assistant will conduct this telephone-screening interview. Interviewee responses will be evaluated by the Principal Investigator of the ongoing clinical trial ([name]), who is Co-Investigator on the current proposal, and a decision regarding study eligibility will be made. Eligible subjects will be scheduled for an in-person visit at the CNRA. The first appointment will begin with the presentation of the informed consent form for the ongoing clinical trial. The consent form will detail the requirements of study participation (e.g., number of visits, type of data collected, time commitment, etc.). Information about the potential risks and how these risks are minimized will be informed. Other information on the consent form will include a full description of study requirements, reimbursement, risks, benefits, alternatives, and the role of the local Institutional Review Board (IRS). All questions will be answered before written consent is requested.

A copy of the signed consent form for the ongoing clinical study is made and given to the subject, another copy is held in the Principal Investigator's ([name]) records, and the original signed consent is kept in a separate, locked file accessible to the IRS upon request.

Subjects for the current DCM MRI proposal will be recruited from participants in the ongoing clinical trial (above). Subjects will be told by the P.I. ([name] [name], or trained research assistant) that the purpose of the current proposed study is to evaluate the mechanism of pharmacotherapeutic response for cocaine addiction treatment using MRI. Information about the potential risks and how these risks are minimized will be given. Other information on the consent form will include a full description of study requirements, reimbursement, risks, benefits, alternatives, and the role of the local Institutional Review Board (IRS). All questions will be answered before written consent is requested.

A copy of the signed form is made and given to the subject, another copy is held in the Principal Investigator's ([name] [name]) records, and the original signed consent is kept in a separate, locked file accessible to the IRS upon request.

## 2.b Protection Against Risk from the proposed DCM MRI study

**Phlebotomy:** This risk will be minimized by having blood drawn by a trained phlebotomist or nurse.

**Contraindication to MRI scanner:** The individuals under this risk will be carefully screened out prior to participation in the MRI experiment by careful history and physical examination.

**Claustrophobia:** This risk will be minimized by having all subjects undergo a "mock" MRI scan using a simulator prior to the actual scan. Subjects with significant claustrophobia during the mock scan will be excluded from the actual MRI study. Subjects will be monitored and can communicate with the scanner operators at all times during scanning. The scanning will be stopped immediately at the subject's request or in case the subject appears uncomfortable.

**Privacy of individuals:** All subject related information will be coded and de-identified. Any information about the subjects gained during the course of the study will remain confidential. Data recorded by paper will be kept in a locked file cabinet in the principal investigator's laboratory. Electronic media (i.e., computer-stored data, and data stored on COs) will be password protected via encrypted code key known only to the study personnel.

**Pregnant women:** Pregnancy will be carefully screened for female subjects. Pregnant women will be excluded from the study.

## 3 Potential Benefits of the Proposed Research to the Subject and Others

All subjects will undergo a free thorough psychiatric and non-psychiatric medical screening during the study. Any clinically relevant abnormalities discovered during this screening will be discussed with subjects and they will be referred for treatment for these abnormalities. All subjects who undergo an MRI scan will have a structural scan read by a Radiologist. Any clinically significant abnormalities on the MRI scans will be discussed with the subjects by the study physician and will be referred for treatment. The optimal measurement of the mechanism of pharmacotherapeutic response has significant implications in cocaine addiction treatment, and would be a great benefit to society.

## 4 Importance of the Knowledge to Be Gained

This study aims to optimally measure the mechanism of pharmacotherapeutic response in dopamine-related neuronal systems underlying impaired cognitive function in cocaine dependence. The completion of the proposed study is expected to improve our understanding of the dopaminergic mechanism and pharmacotherapeutic mechanism in cocaine dependence, and ultimately allow development of a clinically useful biomarker that could be predictive of more time-consuming and costly clinical trial results. Compared to above-stated risks that are minimal, the knowledge to be gained outweighs the risks.

## 5 Data and Safety Monitoring Plan

The Principal Investigator will be responsible of monitoring the safety and efficacy of this study, executing the data and safety monitoring (DSM) plan, and comply with the reporting requirements. The P.I. will provide a summary of the DSM report to NIDA on an annual basis as part of the progress report. The DSM report will include the participants' sociodemographic characteristics, expected versus actual recruitment rates, treatment retention rates, any quality assurance or regulatory issues that occurred during the past year, summary of adverse events (AEs) and serious (SAEs), and any actions or changes with respect to the protocol. The DSM report to NIDA will also include, if applicable, the results of any efficacy data analysis conducted.

All data will be obtained for the specific purposes of this research. We will obtain information about subjects from structured interview evaluations, physical examinations, self-report measures, and collateral informants. The biological specimens obtained from all subjects will include urine, blood, and breath samples. Brain imaging studies will also be performed on all subjects. Collected data will be identified with the study's ID of the participant. The codes that link the name of the participant and the study ID will be kept confidential in a secured cabinet. Data entered by trained research staff will be verified via second entry by independent staff. The study statistician will analyze the data, using SAS software. Primary outcome variables will be derived through vital signs, self-reported behavioral effects, and brain imaging measures.

The following procedures will be taken to safeguard against AEs: (1) careful initial screening to determine eligibility based on inclusion/exclusion criteria; (2) thorough physical evaluation prior to exposure to study drugs consisting of physical examination, standard laboratory tests, electrocardiogram, toxicology screen, pregnancy test and vital signs; (3) careful screening for presence of a pacemaker, metal or electromechanical implants or metallic foreign bodies. Specific criteria will be used to exclude potential subjects for whom MR imaging is contraindicated.

All AEs occurring during the course of the study will be collected, documented, and reported to the Principal Investigator. The occurrence of AEs will be assessed at baseline, on each day of testing, and on visit during the chronic administration phase of the study.

AE's deemed to be serious, as defined by the FDA, will be systematically evaluated on each day of study participation. Any SAE, whether or not related to study, will be reported to the IRB and NIDA. A full written report to all institutions will follow as soon as possible but in no more than three days. The written report will be in the format required by the local IRB and will contain information regarding the date of the SAE, description of the SAE, severity rating (Grade 1 to 4), assessment of cause, whether the SAE indicates an increased risk for current or future subjects, and whether changes to the informed consent form are necessary.

In cases of early termination from the study due to SAE, the participant will have appropriate follow-up medical monitoring. Monitoring will continue until the problem has resolved or stabilized with no further change expected, is clearly unrelated to study medication, or results in death. Outcome of SAEs will be periodically reported to NIDA. A summary of the SAEs that occurred during the previous year will be included in the annual progress report to NIDA.

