**C.4.3 Subject inclusion/exclusion criteria:** The patients who meet DSM-IV criteria for current cocaine dependence, have at least 1 positive urine benzoylecgonine (BE) specimen ( $> 300$  ng/ml) during intake, and are assigned medications or placebo, will be the candidates for this study. In addition, the included subjects must simultaneously meet the following criteria: (a) Be between 18 and 50 years of age; (b) Right handed; (c) Have no past history of Psychiatric or non-Psychiatric medical disorders which could affect the central nervous system as assessed by SCID and physical examination; (d) Be in acceptable health on the basis of interview,

medical history, labs, and physical exam; (e) Be able to understand the consent form and provide written informed consent; (f) Have no metal fragments or other bodily metal (e.g., pacemaker) or significant claustrophobia that would put the subjects at risk for MRI scanning. (For a complete list of inclusion and exclusion criteria see Human Subjects section below).

**C.4.4 Coordination between the Proposed Study and the Clinical Trial:** For eacCD, the MRI session will be conducted in Week 1, which is before the treatment is initialized (baseline pretreatment). The treatment outcome (see Section C.3.4 Treatment Outcome) will be shared for the snDCM study.

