**C.4.6 Response Inhibition Task for fMRI:** An event-related Go/NoGo task [1] is used for fMRI of response inhibition. In each run, the subjects look at a total of 224 visual stimuli that are sequentially presented in random order. Each stimulus is displayed for 500 ms, and any two neighbor stimuli are separated by a blank screen lasting 1900, 2100, or 2300 ms (uttered randomly). Each visual stimulus consists of lines enclosed within two boxes that are presented simultaneously side by side. The subjects are instructed to look at both boxes and to discriminate the direction of the lines. The subjects are instructed to press a button using their right index finger only when they see that both boxes show diagonal lines in the same direction in both boxes (Go trials). The subjects are instructed not to press any button when they see that both boxes show horizontal lines (easy-NoGo trials), or when they see that one box contains diagonal lines that are in the opposite direction of the diagonal lines in the other box (hard-NoGo trials). For Go trials, a correct response is defined as a key-press completed within 600 ms. For NoGo trials, an incorrect response is defined as a key-press completed within 600 ms. There are 168 Go trials (75%), 28 easy-NoGo trials (12.5%), and 28 Hard-NoGo trials (12.5%) in each fMRI run (10 min 40 s per run). For detailed descriptor, please see reference [1].

**C.4.7 Pre- and Post-treatment Behavioral Performance:** Because fMRI sessions in this project are conducted only during pretreatment baseline, this project will also acquire out-of-scanner pre-treatment and post-treatment (week 12) behavioral data for the cognitive tasks. Pre-treatment performance will be considered as a possible confounding factor and will be controlled as a covariate in the statistical analysis (Section C.4.20). Post-treatment behavioral performance is a treatment outcome and will be included in the treatment prediction analysis (C.4.20). In addition, [name], who is an expert in the behavioral science of drug addiction, will be a Consultant on this project to advise on the behavioral data implementation and analysis.

**C.4.8 MRI Scanning Site and Devices:** MRI sessions are conducted at the Magnetic Resonance Imaging Center of the UTHSC-H, using a research-dedicated Philips Intera 3.0 T MRI scanner with an 8-channel receive head coil (Philips Medical Systems, Best, Netherlands).

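### After early termination for an SAE, monitoring may end once the event is judged unrelated to study medication, a test that an unresolved SAE from the pre-dose blood draw or MRI would normally meet

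*Protocol*

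**What the plan says.** Section 5 of the Protocol (Data and Safety Monitoring Plan) makes three statements about SAEs that matter here.

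- Reporting: "Any SAE, whether or not related to study, will be reported to the IRB and NIDA". A written report, including an assessment of cause, follows within three days.
- Follow-up: "In cases of early termination from the study due to SAE, the participant will have appropriate follow-up medical monitoring". That monitoring lasts until the problem has "resolved or stabilized with no further change expected, is clearly unrelated to study medication, or results in death".
- Outcomes: "Outcome of SAEs will be periodically reported to NIDA". No limit by relatedness is attached.

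Section 1.c lists five potential risks: phlebotomy, MRI in people with metal or implants, claustrophobia, loss of privacy, and MRI during pregnancy. On the second it says: "Individuals who have pacemakers, metal or electromechanical implants or metallic foreign bodies can be injured if they undergo an MRI scan". No medication risk is listed.

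On timing, section C.4.4 states that for each cocaine-dependent subject "the MRI session will be conducted in Week 1, which is before the treatment is initialized", and section C.4.7 adds that "fMRI sessions in this project are conducted only during pretreatment baseline". The timeline in section C.4.14 puts screening blood work and HIV testing on Day 1 and the scan on Day 3. Sections C.4.1 and C.4.2 plan 30 medication, 30 placebo and 30 healthy control subjects. The SAP is a data analysis plan and does not address SAE follow-up.

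**The concern.** The follow-up sentence judges relatedness against the study medication only. The harms that section 1.c foresees come mainly from study procedures, at a time when nobody has taken the drug, and one of the three groups never takes it. A participant hurt at the scan or the blood draw who leaves for that reason could have monitoring closed as unrelated to medication while the problem is still open, and the site would be following the plan as written.

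The first thing at stake is the participant's safety follow-up. The second is the completeness of the SAE outcome data: the plan promises outcomes to NIDA, but under this rule the final outcome of such an event may never be observed.

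**Working it through.** No sample-size, power or error-rate figure is involved. The check reads the rule as written and sets it beside the risk list and the schedule.

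**1. Structure of the rule.** The end points are resolution or stabilisation, clear unrelatedness to medication, and death. They are joined by *or*, so meeting any one of them is enough. Unrelatedness to medication can end monitoring of a problem that is neither resolved nor stable.

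**2. Scope of the rule.** It governs only participants whose early termination was due to an SAE. SAEs that do not lead to termination fall outside it.

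**3. Section 1.c risks against dosing.**

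| Risk in section 1.c | Source | Before first dose? |
|---|---|---|
| Phlebotomy | Screening bloods, Day 1 (C.4.14) | Yes |
| MRI with metal or implants | Scan, Day 3 (C.4.14, C.4.4) | Yes |
| Claustrophobia | Scan, Day 3 | Yes |
| MRI in pregnancy | Scan, Day 3 | Yes |
| Privacy | Data handling | Not tied to either procedure and not a medical event |

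The timing argument covers 4 of the 5 risks. Section 5 supports it by placing laboratory tests before exposure to study drugs.

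**4. Who has no drug exposure.** Planned participants: 30 + 30 + 30 = 90. Controls assigned neither drug nor placebo: 30/90 = 33%. For controls, any SAE is unrelated to study medication by design. For the other 60, the same is true of an SAE that occurs at screening or at the scan. These figures count people, not events; the documents give no expected SAE rate.

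**5. Result of steps 1 to 4.** Take an SAE caused by the blood draw or the MRI, unresolved, and leading to early termination before dosing. It normally satisfies the medication test at once, so the plan permits monitoring to stop.

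**6. Comparison within section 5.** AEs are assessed at baseline and on testing days as well as during dosing. SAEs are reported whatever their relation to the study. Outcome reporting has no relatedness limit. Only the end-of-monitoring sentence narrows to medication.

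**7. Does another section close the gap?** Section 2.b covers prevention: screening out, the mock scan, and halting the scan on request. Section 3 covers referral of abnormalities found at screening or on the structural scan. Neither covers continued follow-up of someone harmed by a procedure.

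**The case against.** The best defence is that the practical exposure is small and the text is milder than it first looks. Most of that stands.

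- **The named risks would seldom be serious.** Section 1.c describes phlebotomy harm as bruising and claustrophobia as anxiety. People with implants or metal are screened out, pregnancy is tested just before the scan, and those with marked claustrophobia at the mock scan are excluded. This makes events rare; it does not change what the rule allows when one occurs.
- **The rule permits an end and does not order one.** The preceding sentence promises appropriate monitoring. A reader might infer that follow-up is dropped for every risk in section 1.c. The documents do not support that: stopping is optional, the rule applies only after early termination for an SAE, and privacy is outside the argument.
- **Reporting is untouched.** A reader might infer that procedure-related SAEs would go unreported, or that their outcomes would necessarily be missing. The duty to report the SAE and its outcome remains. The weakness is that an outcome may not be known if monitoring stopped early.
- **Reporting and follow-up may properly use different tests.** True in general, and the difference alone would not show an error. Here it matters because the narrower test concerns an exposure absent from the section's own risk list.
- **The minimal-risk statement in section 4.** A reader might infer that this statement is undermined. It is not: it is a prospective judgement and does not depend on SAE outcomes collected later.

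**Conclusion.** The concern holds in a narrow form. As written, section 5 permits monitoring of an unresolved SAE from a study procedure to end after early termination, because the test refers only to medication, while four of the five risks in section 1.c arise before dosing and the 30 controls receive no drug. This is a stated rule that could give a worse safety result if followed exactly, rather than a missing detail.

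The size is modest. It cannot be expressed as a percentage of SAEs, because the documents give no event rate and the rule covers only SAEs that cause early termination. The one-third share of controls describes how many people can never have a medication-related event, not how many would be affected.

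The conclusion rests on two assumptions. One is that blood draws occur only at screening; the Protocol describes no later ones but does not expressly exclude them. The other is that the event appears, and is judged, before dosing or in a control. An SAE that emerges after dosing in a treated participant might not be called clearly unrelated to the drug.

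**What to change.** Reconcile the relatedness test in the end-of-monitoring sentence of section 5 with the procedure risks in section 1.c and with the study-wide scope of the SAE reporting rule in the same section. The aim is that being unrelated to medication does not, by itself, close monitoring of an SAE arising from a study procedure. The sponsor and the IRB should decide the exact follow-up rule; no wording is proposed here.

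The cost is an edit to one sentence of the monitoring plan, with no effect on sample size, schedule or analysis. The downside is occasional longer follow-up of a rare event.
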